5.1. General Considerations

Except where otherwise specified, the following general principles apply to the planned statistical analyses. All statistical analysis will be conducted using {SAS version 9.3 or later (SAS Institute Inc., Cary, NC)} or other widely accepted statistical or graphical software as required.

5.1.1. Descriptive Statistics

Continuous variables will be summarized with mean, standard deviation, median, max, min, and number of evaluable observations. Categorical variables will be summarized with frequency and percentages. Confidence intervals may be presented where appropriate using the t-distribution for continuous variables and Clopper - Pearson Exact method for categorical variables.

5.2. P-Values

Unless otherwise specified, statistical analyses will be performed using a two-sided hypothesis test at the overall 5% level of significance. P-values will be rounded to three decimal places. If a p-value is less than 0.001 it will be reported as "< 0.001." If a p-value is greater than 0.999 it will be reported as "> 0.999."

6. References

- ICH Guidelines. E9: *Statistical Principles for Clinical Trials* <http://www.ich.org/ich5e.html>.
- Adaptive Designs for Clinical Trials of Drugs and Biologics Guidance for Industry November 2019; <https://www.fda.gov/regulatory-information/search-fda-guidance-documents/adaptive-design-clinical-trials-drugs-and-biologics-guidance-industry>

7. Appendix 1 - LED Calculation

LED Used for Parkinson's Studies- 28Jan2020

Reference Tomlinson article Table 2 or order in calculating the LED.

Medication	Conversion Factor (mg)	
Levodopa (immediate release)	X 1	
Levodopa CR (controlled release)	X 0.75	
Levodopa ER (extended release) "Rytary"	X 0.5	
Entacapone (or Stalevo™)	LD x 0.33	
Duodopa™	X 1.11	"When entering dose, consider total mg infused per day"
Pramiprexole	X 100	
Ropinirole	X 20	
Rotigotine	X 30	
Selegiline (oral)	X 10	
Selegiline (sublingual)	X 80	
Cabergoline	X 100	
Rasagiline	X 100	
Amantadine	X 1	
Apomorphine	X 10 (total mg per day)	"When entering dose, consider total mg infused per day"
Bromocriptine	X 10	
Pergolide	X 100	
Benzhexol	No L-dopa equivalent	

Benzotropine	No L-dopa equivalent	
Biperiden	No L-dopa equivalent	

Tomlinson et al. Systematic Levodopa Equivalent Review in Parkinson's Disease. *Movement Disorders* (2010).

Rytary Instructions for Use Label – Table 1

8. Appendix 2 – Statistical Tables (see attachment)

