3.2. Hypothesis & Primary Endpoint

Primary Endpoint: The change in MDS-UPDRS Total score at 4 months from baseline defined as sections I, II, III and IV in PwP. The endpoint will be compared between those who are treated with standard of care and PKG data (PKG+ Group) and those who are treated per standard of care alone (PKG- Group).

The primary endpoint of change in total MDS-UPDRS at 4 months will be compared between the treatment group (PKG+ Group) and the control group (PKG- Group) based on a two-sample t-test. In the event normality assumptions are violated, a non-parametric analog will be used. A difference between groups of 5 points is assumed for the change in total MDS-UPDRS as well as a standard deviation of 13 based on historical data. With these assumptions, a sample size of 280 evaluable subjects will provide approximately 83% power for the statistical hypothesis test for the primary endpoint. To account for attrition of up to 20%, a total enrollment of 350 subjects is planned. Enrollment was stopped in the study at 41 subjects enrolled. These 41 subjects will be followed through the 4-month endpoint and will be analyzed.

The difference in the primary endpoint between randomized groups will be compared with a two-sample t-test of means at the 1-sided alpha of 0.025 (equivalent to a two-sided 0.05 alpha level). In the event normality assumptions are violated, a non-parametric analog will be used.

The primary analysis will be based on the intent-to-treat (ITT) population defined as all randomized subjects analyzed according to the treatment group assigned. Except where otherwise specified, the following general principles apply to the planned statistical analyses. All statistical analyses will be conducted using SAS version 9.4 or later (SAS

Institute Inc., Cary, NC) or other widely-accepted statistical or graphical software as required. Continuous variables will be summarized with mean, standard deviation, median, max, min, and number of evaluable observations. Categorical variables will be summarized with frequency and percentages. Confidence intervals may be presented where appropriate using the t-distribution for continuous variables and Clopper-Pearson Exact method for categorical variables. Unless otherwise specified, statistical analyses will be performed using a one-sided 0.025 alpha level.

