An additional analysis will be conducted due to impacts from COVID-19 for the primary endpoint. This will include looking at instances where a partial UPDRS Part III was collected due to restrictions when conducting a telehealth video visit.

Subgroup Analysis of Primary Endpoint

Subgroup analyses will be conducted to examine the possible influence of baseline characteristics on the primary outcome. Subgroups of interest may include but are not limited to:

- Duration of disease – defined by years of disease (Date of Visit 1 - Year of PD Diagnosis)
- Stage of PD - defined by Hoehn & Yahr (1-5) at Visit 1
- History of fluctuation – defined by patient wearing off in last 30 days at Visit 1
- Gender
- Age – defined by Date of Visit - DOB
- Controlled PD at Baseline Visit in PKG+ and PKG- groups as defined by the PKG for both groups.
- Uncontrolled PD at Baseline Visit in PKG+ and PKG- groups as defined by the PKG for both groups.

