4.5. Analysis Populations

The primary analysis will be based on the intent-to-treat (ITT) population defined as all randomized subjects analyzed according to the treatment group assigned.

In addition, analyses based on the per-protocol (PP) population will be performed for the primary and secondary endpoints. The PP population is defined as all subjects who are randomized and adhere to the study protocol requirements, including: meeting all of the subject selection criteria, completion of the PKG Watch wear period, inability for investigator to further make treatment changes due to known contraindication, completion of subject surveys and completion of follow-up visits.

Subject selection criteria can be found in the study protocol.

5. Methods

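### The SAP's default 5% level is called *overall* and contradicts a second default in SAP 3.2; it holds for the single primary test, but not across the unadjusted secondary, per-protocol and open-ended subgroup analyses

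*SAP*

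**What the plan says.** There is one primary endpoint (SAP 3.2): "Primary Endpoint: The change in MDS-UPDRS Total score at 4 months from baseline defined as sections I, II, III and IV in PwP". It has its own test and level: "two-sample t-test of means at the 1-sided alpha of 0.025 (equivalent to a two-sided 0.05 alpha level").

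The SAP then sets two defaults for everything else:

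- SAP 3.2: "Unless otherwise specified, statistical analyses will be performed using a one-sided 0.025 alpha level".
- SAP 5.2, also subject to anything specified otherwise: "statistical analyses will be performed using a two-sided hypothesis test at the overall 5% level of significance".

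The non-primary analyses that fall under those defaults are:

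- Nine numbered secondary items in SAP 3.4. Item 1 is a comparison of responder percentages for the two arms. Most of the others describe within-subject change and improved/same/worsened summaries, with no between-arm test named.
- A second population (SAP 4.5): "analyses based on the per-protocol (PP) population will be performed for the primary and secondary endpoints".
- Subgroup analyses of the primary endpoint (SAP 3.2), introduced by "Subgroups of interest may include but are not limited to". Seven entries follow. Two of them, controlled and uncontrolled at baseline, are the two levels of one factor. No treatment-by-subgroup term is specified.

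Neither the protocol nor the SAP gives a testing order, an alpha split, a multiplicity adjustment, or a statement that non-primary p-values are exploratory. SAP 4.1 records that enrollment stopped at 41 subjects, before any interim analysis milestone.

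**The concern.** An overall level normally means the chance of any false positive across a set of tests. Attached as the default to all analyses, with no adjustment, that description is true only if a single test is run, and the SAP plans more than one. The subgroup list has no upper bound, so the size of the set cannot even be fixed.

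The two defaults also disagree. For a secondary p-value, SAP 3.2 would count only one direction at 0.025, and SAP 5.2 would count both directions at a total of 5%. Two analysts following the same SAP could report different p-values for the same outcome.

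At stake is what the trial may conclude. With 41 subjects the primary comparison is likely to miss the effect it was designed for. A secondary or subgroup p-value below 0.05 would then attract attention, and the wording of SAP 5.2 would lend it an error guarantee that the plan does not provide.

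**Working it through.** **1. The stated 5%.** For k independent tests, each at level α, the chance of at least one false positive is 1 − (1 − α)^k.

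- k = 1: 1 − 0.95 = 0.05. The SAP's figure reproduces for the primary test alone.
- k = 2: 1 − 0.95² = 0.0975. It already fails.

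**2. How many non-primary outcomes.** SAP 3.4 numbers 9 items. Counting each distinct outcome once gives 13: responders; MDS-UPDRS Part III; BKS; DKS; PDQ-39; Parts I, II and IV; PTT; FDS; PTI; LED; and the patient survey. Per-protocol repeats and subgroups are left out, the first because they re-test the same hypotheses and the second because the list is open.

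**3. Chance of at least one false positive, if each outcome is tested between arms at two-sided 5%.** The independent row uses the formula above. The correlated rows come from 20,000 simulated trials of 21 against 20 subjects, with two-sample t-tests on 39 degrees of freedom and the same correlation between every pair of outcomes. The documents give no correlations, so these are assumptions.

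| Correlation | 9 items | 13 outcomes |
|---|---|---|
| 0 | 1 − 0.95^9 = 37.0% | 1 − 0.95^13 = 48.7% |
| 0.5 | 27.2% | 34.2% |
| 0.8 | 16.9% | 19.8% |

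The lowest entry is still more than three times 5%.

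**4. Does the choice of default matter?** Under the SAP 3.2 default (one-sided 0.025), the independent figures are 1 − 0.975^9 = 20.4% and 1 − 0.975^13 = 28.1%. These count false positives in one direction only. The two defaults therefore give different answers, and neither gives 5%.

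**5. Power of the primary test at the actual size.** Inputs from SAP 3.2: "A difference between groups of 5 points is assumed for the change in total MDS-UPDRS as well as a standard deviation of 13". Assume 21 against 20 subjects, all evaluable.

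- Standard error = 13 × √(1/21 + 1/20) = 4.06.
- Noncentrality = 5 / 4.06 = 1.23, on 39 degrees of freedom.
- Power at two-sided 5% = 22.5%.
- With the SAP's 20% attrition (41 × 0.8 ≈ 33, so 17 against 16), power = 18.8%.
- The difference detectable with 80% power, with all 41 evaluable, is about 11.7 points.

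A side note on the same formula: with 140 per arm it gives 89.4%, not the roughly 83% that SAP 3.2 states. A two-sided 0.025 test gives 83.2%. That is a separate matter and does not affect the multiplicity result.

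**The case against.** The strongest reply is that the plan's only confirmatory test is sound. There is one primary endpoint with its own alpha, no interim milestone was reached, and no success criterion is attached to any secondary endpoint. *Overall* may be stock wording for the total two-tailed level of each test. The subgroup paragraph speaks of examining possible influence, which is exploratory in tone. Most secondary items describe summaries, and the lead-in to SAP 3.4 speaks of comparing visits rather than arms. SAP 5.2 sets the level for tests that are run; it does not require a test for every summary.

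Much of this stands. A reader might infer that the trial's error rate has failed as a whole; the documents do not support that, because the primary test keeps its 5%.

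A reader might also count more than 20 comparisons and quote 69%. That takes 23 independent tests: 1 for responders, 3 for Part III, BKS and DKS, 9 for the PDQ-39 index and its 8 dimensions, 3 for Parts I, II and IV, 3 for PTT, FDS and PTI, and 4 for LED across visits. The SAP says that the PDQ-39 dimensions are calculated and that LED change is compared by visit for each patient. It names no between-arm test for any of them. The index is built from its dimensions and LED at successive visits overlaps, so independence is not plausible either.

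Finally, a reader might cite the width of a small subgroup's interval: 20.6 points either side for 9 subjects, if 22% are in target as in the cohort cited in the protocol's introduction. That shows imprecision, not an inflated error rate, and the 22% comes from a population with low access to specialist care.

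What the reply does not remove is the text itself. Item 1 is an explicit comparison of arms, per-protocol analyses are planned for all secondary endpoints, the subgroup list is open, and whenever a p-value is produced one of two conflicting defaults applies.

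**Conclusion.** The concern holds as a defect of wording and scope. The level called *overall* in SAP 5.2 is a property of the single primary test only, and SAP 3.2 and 5.2 give different defaults that must be reconciled.

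If each non-primary outcome is tested at 5%, the chance of at least one false positive is about 37% to 49% under independence, 27% to 34% at correlation 0.5, and 17% to 20% at 0.8, for 9 and 13 outcomes respectively. These figures assume one between-arm test per outcome, all null hypotheses true, and equal correlation. The actual number of p-values cannot be settled from the text available, since most items name no test and the Appendix 2 tables are an attachment not included there.

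The conclusion does not depend on the exact count, because any two unadjusted tests exceed 5% unless they are perfectly correlated. Its practical weight comes from power of about 22% for the primary comparison with 41 subjects, on the SAP's own effect and standard deviation.

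**What to change.** In SAP 3.2 and SAP 5.2, state the same default: two-sided 5%. Protocol 6.4 carries the one-sided wording too, so the SAP should record the change. It does not alter the primary critical value in the direction of benefit.

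In SAP 5.2, drop *overall* and limit the 5% level to the intent-to-treat primary comparison. Report secondary, ancillary, per-protocol and subgroup results as between-arm estimates with 95% confidence intervals. Label any p-value as nominal and make no significance claim from it.

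In the subgroup paragraph of SAP 3.2, delete the clause that leaves the list open. Examine each listed characteristic in its own separate model with a treatment-by-characteristic term, labelled exploratory:

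- age and disease duration as continuous variables;
- Hoehn & Yahr as a linear or collapsed term;
- controlled versus uncontrolled as one two-level factor.

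A single model holding every interaction is not workable with 41 subjects.

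The cost is SAP wording and table footnotes, with no new data. The sponsor gives up significance claims on non-primary results.
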